The study duration for individual participants will be at least approximately 284 weeks, including an 8-week screening period, a double-blind treatment period of at least 260 weeks in length, a 4-week final dose visit, and a final safety follow-up visit 16 weeks after the last dose of study drug (crenezumab or placebo) that will allow for clinical follow-up after treatment discontinuation for participants who do not continue with study drug beyond the end of Study Period A or who terminate study drug early. One or more interim analyses may be performed at the Sponsor's discretion (see Sections [3.2](#) and [4.10.9](#)).

Study Period B: Following the completion of Study Period A, participants will be offered the opportunity to continue to receive study drug until *regulatory approval or another mechanism for post-trial access to crenezumab* is started (via an OLE or other programs) or development of crenezumab is discontinued. This is termed Study Period B (see Sections [3.2.1](#), [4.5.5](#), [4.5.8](#)). All *PSEN1* mutation carriers will be provided crenezumab in Study Period B regardless of treatment allocation during Study Period A and all non-carriers will continue on placebo. Treatment allocation for both Study Periods A and B will remain blinded. Study Period B may last up to approximately 3–3.5 years depending on when participants enter Study Period B and when crenezumab is granted *regulatory approval or development of crenezumab* is discontinued. See [Figure 2](#).

See [Appendix 1](#) and [Appendix 2](#) for the study flowchart for SC dosing.

[figure not shown]
See [Appendix 3](#) and [Appendix 4](#) for the study flowchart for IV dosing.

Figure 1 Study Design

PSEN1 = presenilin 1; RCT = randomized, controlled trial.

Figure 2 Study Schematic

3.2

RATIONALE FOR STUDY DESIGN

Study Period A: The study will utilize a common-close design. All participants will be enrolled in the double-blind portion of the study until the last ongoing participant who is enrolled in the study and remains on treatment (i.e., ongoing enrolled participant) has received approximately 260 weeks of treatment, as far as is practical (see Section 4.5.4). All participants will not have the same amount of follow-up after enrollment but all will have at least 5 years of double-blind treatment.

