If a participant discontinues from the study (ET) or discontinues from study drug treatment and elects to no longer stay in the study, ET Visit A should be completed if the last visit occurred more than 12 weeks after functional, behavioral and cognitive assessments were performed; ET Visit B should be performed if the last visit occurred within 12 weeks of functional, behavioral and cognitive assessments. The final safety follow-up visit should be scheduled 16 weeks from last dose.

Study Period B: If a participant enters Study Period B, but wishes to stop study treatment before the end of Study Period B, a safety follow-up visit should be completed 16 weeks from the last dose.

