Single 12-Lead ECG ⁱ				x		x	x	x
Physical and neurologic examinations ^j				x		x		x
Serum chemistry and hematology ^{k,l}				x		x		x
MRI ^m						x		
Optional CSF ^{n,p}						x		
Optional Tau-PET ^{o,p}						x		
Amyloid-PET ^p						x		
Evaluate criteria for MCI/AD			x	x	x	x	x	
GDS ^{q,r}			x	x	x	x	x	

Appendix 5
Study Flow Chart for Study Period B: SC Dosing (cont.)

	W1 and Every 2 Weeks Thereafter ^a	W13	W25	W53	W77	W105	W157 and Every 52 Weeks Thereafter	ET/SFU Last Dose + 16 W ^b
Assessment window	(±7d)	(±7d)	(±7d)	(±7d)	(±7d)	(±7d)	(±7d)	(±7d)
SMC ^{q,r}			x	x	x	x	x	
API ADAD Cognitive Composite Battery ^s			x	x	x	x	x	
FCSRT ^s			x	x	x	x	x	
Trail Making Tests A and B ^s			x	x	x	x	x	
RBANS ^s			x	x	x	x	x	
SPCQ ^{u,r,t}			x	x	x	x	x	
CDR ^{q,r,t}			x	x	x	x	x	
FAST ^{r,t}			x	x	x	x	x	
NPI ^{r,t}			x	x	x	x	x	
Suicidality assessment ^{q,r}			x	x	x	x	x	
Study drug administration ^{v,w,x}	x	x	x	x	x	x	x	
Concomitant medication review ^r	x	x	x	x	x	x	x	x
Adverse event review ^r	x	x	x	x	x	x	x	x

AD = Alzheimer's disease; ADA = anti-drug antibody; ADAD = autosomal-dominant Alzheimer's disease; CDR = Clinical Dementia Rating; CERAD = Consortium to Establish a Registry for Alzheimer's Disease; CSF = cerebrospinal fluid; d = day; ET = early termination; FAST = Functional Assessment Staging of Alzheimer's Disease; FCSRT = Free and Cued Selective Reminding Test; GDS = Geriatric Depression Scale; MCI = mild cognitive impairment; MMSE = Mini-Mental State Examination; MRI = magnetic resonance imaging; NPI = Neuropsychiatric Inventory; PD = pharmacodynamic; PET = positron emission tomography; PK = pharmacokinetic; RBANS = Repeatable Battery for the Assessment of Neuropsychological Status; SFU = safety follow-up; SMC = Subjective Memory Checklist; SPCQ = Study Partner Characterization Questionnaire; W = week.

Appendix 5
Study Flow Chart for Study Period B: SC Dosing (cont.)

- ^a Week 1 is the first dose in Study Period B and may occur on the same day as the final ET-A or ET-B visit in Study Period A after all ET assessments are completed and the investigator deems dosing is appropriate.
- ^b Early termination visit/SFU visit, occurring when someone terminates prior to the end of the Study Period B, should be done 16 weeks after the last dose of study drug. Participants who continue crenezumab treatment after the end of Study Period B will not have a “last dose + 16 weeks visit”.

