$$\lambda[c] = \frac{\left(\hat{V}(\hat{\beta}_x[c]) \right)^2}{\left(\hat{V}_{cren}^{comp} \right)^2 + \left(\hat{V}_{pbo,MAR} \right)^2}.$$

We will then perform the imputation based on $c=0$. This scenario assumes that the mean slope from the participants with missing values from the crenazumab arm is the same as the estimated overall placebo slope. We note that this assumption is already conservative in estimating the treatment effect because it implicitly assumes participants

on treatment will even do worse than an average placebo participant, after dropping out of the study.

DELAYED-START ANALYSIS MODEL FROM SECTION 5.10.1.1

The statistical model for this delayed-start analysis can be written as:

$$Y_{ij} = \alpha + (\text{Randomization Factors})_i + u_{0i} + (\beta + \beta_x I_{x,i} + u_{1i})t_{ij} + (\beta_{x,B/CAST} t_{ij} - \beta_{x,B/OLE} T_i)(1 - I_{x,i})I_{t_{ij} > T_i} + \epsilon_{ij},$$

where β_x quantifies the crenezumab annualized treatment effect in slowing down the disease progression in Period A of Study GN28352 and $\beta_{x,B/OLE}$ quantifies the treatment effect by switching from placebo to crenezumab in Period B of Study GN28352 and the OLE; T_i represents the time of the first endpoint assessment after participant i enters into Study Period B or the OLE.

Due to the common-close design of Study GN28352, mutation carriers will have varied duration of follow-up at the end Study Period of A. To calculate the crenezumab treatment effect at the end of Study Period A, we first calculate the arithmetic mean of duration in Study Period A (last endpoint assessment date – randomization date in Study Period A + 1) among mutation carriers and we call this duration \bar{T}_1 . On average, the treatment benefit in slowing down the disease progression at the end of Study Period A can be written as:

$$\Delta_1 = \beta_x \bar{T}_1.$$

Similarly, we also calculate the arithmetic average of overall duration at the end of the OLE among mutation carriers and we call this duration \bar{T}_2 . The average treatment benefit remained at the end of OLE can be written as:

$$\Delta_2 = (\beta_x - \beta_{x,B/OLE}) \bar{T}_2 + \beta_{x,B/OLE} \bar{T}_1.$$

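### The delayed-start model and its Delta2 formula place the former-placebo slope change at different times, so retained benefit is understated if crenezumab helps the delayed-start arm

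*SAP*

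**What the plan says.** **Model (SAP Appendix 3, delayed-start analysis).** Carriers randomized to placebo get an added slope, written here as `beta_B`, only at times later than T_i. The SAP says T_i "represents the time of the first endpoint assessment after participant" i enters Period B or the OLE.

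**Summary quantities (same appendix).** For the length of Period A, "we first calculate the arithmetic mean of duration in Study Period A", taken as last endpoint assessment date minus randomization date plus one day, among mutation carriers (`T1bar`). The benefit at the end of Period A is `Delta1 = beta_x * T1bar`. "The average treatment benefit remained at the end of OLE can be written as" `Delta2 = (beta_x - beta_B) * T2bar + beta_B * T1bar`, with `T2bar` the mean overall duration. Retention is declared if the lower 90% confidence limit of `Delta2` minus 50% (or 30%) of `Delta1` exceeds zero.

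**Intended time of change (SAP 5.10.1.1).** The former-placebo slope is described as different in Period B and the OLE, not as different from the first assessment made there.

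**Schedule (Protocol Appendices 5 and 6).** Footnote a: "Week 1 is the first dose in Study Period B and may occur on the same day as the final ET-A or ET-B visit". The row "API ADAD Cognitive Composite Battery ^s" and the FCSRT row are blank at W1 and W13 and marked at W25, W53, W77, W105 and W157, for both SC and IV dosing.

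**The concern.** A piecewise-linear model has one knot, and any contrast derived from it must use that knot. Here the model uses T_i and the contrast uses `T1bar`. Because the tested scores are not collected at Period B entry, T_i falls about half a year after former placebo carriers start crenezumab.

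This has two consequences. If the slope changes at the switch, a late knot assigns the first half-year on crenezumab to the placebo slope, which lowers `beta_x` and raises `beta_B`. In either case, `Delta2` multiplies `beta_B` by the whole span from `T1bar` to `T2bar`, although the fitted term covers only the part after T_i.

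SAP 5.10.1.1 limits formal delayed-start testing to the API ADAD composite and the FCSRT Cueing Index, in a fixed sequence that stops at the first failure. A shortfall at an early step can therefore close later steps, and the reported retention is off whatever the test result.

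**Working it through.** The plan gives no numerical value for `Delta2`, so what can be checked is whether the formula follows from the model.

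**1. Algebra.** At time `T2bar` the crenezumab mean has risen by `(beta + beta_x) * T2bar` and the former-placebo mean by `beta * T2bar + beta_B * (T2bar - mean(T_i))`. The difference is

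`beta_x * T2bar - beta_B * (T2bar - mean(T_i)) = (beta_x - beta_B) * T2bar + beta_B * mean(T_i)`.

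The SAP's `Delta2` is reproduced only if `mean(T_i) = T1bar`. Otherwise it is off by `-beta_B * (mean(T_i) - T1bar)`.

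**2. The gap.** First Period B dose at W1 and first scores at W25 give 24 weeks, about 0.46 years. Section 4.5.6 of the protocol adds: "ET Visit B should be performed if the last visit occurred within 12 weeks of functional, behavioral and cognitive assessments". If those scores are not repeated at ET-B, the last score can be up to about 12 weeks older, giving a gap of up to about 36 weeks (0.69 years). A missed W25 visit moves T_i to W53.

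**3. Size if the slope really changes at T_i.** With `beta_B = beta_x`, the error as a share of `Delta1` is the gap divided by `T1bar`. Protocol section 3.2 gives the lower end ("but all will have at least 5 years of double-blind treatment") and SAP 5.3.4 the upper end, Year 8.

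| T1bar (years) | 24-week gap | 36-week gap |
|---|---|---|
| 5 | 0.46/5 = 9.2% | 0.69/5 = 13.8% |
| 6.5 | 7.1% | 10.6% |
| 8 | 5.7% | 8.6% |

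**4. Size if the slope really changes at the switch.** This uses a noise-free generalized least squares fit of the random-slope model. Assumptions: Period A ends spread evenly over weeks 260, 312, 364 and 416 (mean 338 weeks, `T1bar` = 6.478 years). Period B visits fall 24, 52, 76 and 104 weeks after the switch (`T2bar` = 8.471), in line with the data snapshot planned 2 years after the last Period A efficacy visit. There is no dropout, and slopes are linear.

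With true `beta_x = beta_B = 1`, the fit returns `beta_x` = 0.972 and `beta_B` = 1.244. Then

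- `Delta1` = 0.972 × 6.478 = 6.297
- `Delta2` = (0.972 - 1.244) × 8.471 + 1.244 × 6.478 = 5.754
- retention = 5.754 / 6.297 = 0.914, against a true 1.00.

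Four other sets of variance components gave 0.913-0.914. With every `T1bar` at 5 years the result was 0.896, and with 3 years of Period B it was 0.922.

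**5. Other delayed-start effects, same setting.** True retention is `(8.471 - r × 1.993) / 6.478`, where `r = beta_B / beta_x`.

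| r | True | SAP as written |
|---|---|---|
| -0.5 | 1.46 | 1.50 |
| 0 | 1.31 | 1.31 |
| 0.5 | 1.15 | 1.11 |
| 1 | 1.00 | 0.91 |
| 1.5 | 0.85 | 0.71 |
| 2 | 0.69 | 0.50 |
| 3 | 0.39 | 0.06 |

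**6. Candidate corrections at r = 1.** Moving the knot to the switch returns 1.00 when the slope changes there. Keeping T_i and using `mean(T_i)` in the `beta_B` term returns 1.005 when the slope changes at the switch. When the slope changes at T_i, it returns the true 1.071, where the formula as written gives 1.00.

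**The case against.** **A lag may be intended.** Protocol section 1.2.2.2 reports that steady-state troughs in the Phase II studies were reached between Week 13 and Week 25, so a delayed onset is plausible. This does not rescue the formula: if T_i is a deliberate lag, `Delta2` is still wrong by the amount in step 3. The lag does count against one of the corrections. With a true 24-week lag, a knot at the switch overstates retention slightly (0.86 against 0.83 at r = 2). The SAP as written gives 0.69 there, further from the truth.

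**The error is conservative and, in the natural case, moderate.** This stands. At r = 1 the formula gives 0.91, far above both margins. A reader might infer from the lower rows of the table that the 50% margin is in danger in general. Those rows need switchers to gain two or three times the early-start effect, and the documents give no reason to expect that. The fit is also noise-free. It shows bias in the estimate, not how often the test decision would change.

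**Two other stronger readings do not hold.** A reader might infer that retention is always understated; the direction depends on `beta_B > 0`. A reader might also take this to be the only formally tested Period B claim. SAP 5.10.1.2 gives two-sided p-values for two time-to-event endpoints, and the delayed-start sequence itself is in Figure 5, which is not shown. If the sponsor terminates the study on the Period A results, Protocol 4.10 and SAP 5.10 make all Period B analyses exploratory.

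**Conclusion.** The inconsistency is real. The `Delta2` formula does not follow from the model beside it, whether the slope changes at the switch or at T_i.

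When `beta_B > 0`, the premise of a delayed-start design, retained benefit is understated. With `beta_B = beta_x` the shortfall is about 6-9% of `Delta1` at a 24-week gap, and up to about 14% at 36 weeks with the shortest Period A. It grows only if switchers gain more than early starters, vanishes at `beta_B = 0` and reverses below that. For `beta_B > 0` it costs power and does not inflate type I error.

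The figures rest on the assumed spread of Period A durations, attendance on schedule, linear slopes, no dropout, and reading the two labels `beta_x,B/CAST` and `beta_x,B/OLE` as one parameter. The issue does not touch the Period A primary analysis. It is worth correcting because the remedy is small.

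**What to change.** Make the model and `Delta2` use the same time. Either option works:

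- Define T_i as the time of the first Period B dose (the end of Period A), apply the added slope to all later assessments, and compute `T1bar` from that T_i.
- Keep T_i as it is, and replace `T1bar` with `mean(T_i)` in the `beta_B` term of `Delta2` only.

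The first matches the description in SAP 5.10.1.1, at the price of the slight overstatement noted above if onset is delayed. The second leaves the fitted model unchanged.

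Changing the knot definition alone is not sufficient. Period B is optional (Protocol 3.2.1), so some carriers have no T_i. State which carriers enter each mean, use the same set throughout, and give a rule for those who do not enter Period B. Express the means in years, to match the slopes. Use one label for the Period B slope parameter.

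The cost is a few lines in SAP Appendix 3. Dose and assessment dates are already collected, and no visit or procedure changes.

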The common-close design will increase the power of detecting a difference between crenezumab and placebo by utilizing the data obtained from each participant, including those data from participants with more than 5 years' treatment duration, in the overall analysis. Furthermore, the common-close design allows similar duration of treatment with the higher IV dose (60 mg/kg IV) or matching placebo, for analysis of treatment at a higher dose.

The rationale for changing the study design is to maintain statistical power of 80% to detect a treatment effect (see Section 4.10 for further details)—despite the fact that only 252 participants of the 300 originally planned could be recruited from this kindred—and to allow reasonable duration of treatment for assessment of benefit at the higher dose.

Study Period A will be continued until the last ongoing enrolled participant has reached 260 weeks, as far as is practical (see Section 4.5.4).

One or more interim analyses may be conducted at the Sponsor's discretion at any point during the study. Such an analysis may be triggered by, for example, the availability of results from another clinical study with crenezumab.

3.2.1

Rationale for Study Period B

For the first participants reaching the final efficacy visit in Study Period A (End of Treatment-A or End of Treatment-B visit), several months will pass before results from Study Period A are available *and a longer period of time until regulatory approval or a mechanism of post-trial access is set up*. To honor the long commitment of participants and not to force a treatment gap in the case crenezumab is effective in slowing disease progression, participants will be offered the opportunity to continue to receive blinded study drug until *regulatory approval or post-trial drug access is started* (via an OLE or other program) or there is a decision to terminate the development of crenezumab on the basis of the results in Study GN28352. *Data collected in Study Period B will be used to assess the long term safety and efficacy of crenezumab.* Continuation into Study Period B is optional.

Treatment and Dosing

After completing the final efficacy visit in Study Period A, all mutation carriers who enter Study Period B will receive crenezumab and all non-carriers entering Study Period B will continue to receive placebo. Participants, site staff, vendor staff, and Sponsor will

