3. SAMPLE SIZE DETERMINATION

This study will enroll up to 300 participants: up to 200 participants will be enrolled in the carrier cohort and up to 100 participants will be enrolled in the non-carrier cohort. Participants in the carrier cohort will be randomized in a 1:1 randomization ratio to active treatment or placebo. The study was initially powered to compare the mean change from baseline over 260 weeks in the API ADAD Composite Cognitive Test total score between the active treatment group and the placebo group. Assuming a 25% dropout rate with use of two-sided testing at the overall 0.05 level, a placebo group coefficient of variation of 65% for the Week 260 change scores ($= 100\% \times$ standard deviation of

[figure not shown]
placebo participant change scores/mean of placebo participant change scores) and 100 participants per arm, the study will have at least 80% power to detect a true effect of 30% reduction of the mean decline in the API ADAD Composite Cognitive Test total score in the placebo group using a t-test. Participants in the non-carrier cohort will all receive placebo and will be included in the study in order to maintain the genotype blind.

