5.10.1 Efficacy Analyses

All efficacy analyses will include data from Study Period A, Study Period B, and the OLE study; the analysis population will be based on mITT. *The delayed start efficacy analyses will be triggered 2 years after the last efficacy visit in Study Period A.*

Two types of efficacy analyses are prespecified depending on the endpoint type: delayed-start analyses for continuous endpoints and rank-preserving structural failure time (RPSFT) analyses for time-to-event endpoints.

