5.10.1.1 Delayed-Start Analyses

The delayed-start analysis will be used for all continuous efficacy endpoints that will be collected in Study Period B and the potential OLE study. Since the potential OLE will not be published by the finalization of this SAP, the description in this section is in general terms and does not focus on any specific endpoint. However, statistical testing will be performed only on the API ADAD Composite Cognitive Test total score and the FCSRT Cueing Index. Other continuous efficacy endpoints, including clinical endpoints, fluid biomarkers, and imaging biomarkers, will be considered exploratory and thus, formal statistical testing will not be done.

Figure 4 illustrates the concept of the delayed-start analysis. As shown in the figure, a treatment effect is assumed in Period A of Study GN28352; the disease progression slope of mutation carriers from the Study Period A crenezumab arm is assumed to be the same in Study Period B and in the OLE; the disease progression slope of mutation carriers from the Study Period A placebo group; however, will have a different slope in Study Period B and in the OLE. The statistical model details can be found in

Appendix 3. To control the type I error within the delayed-start analyses, the fixed testing sequence is specified in the following figure. The α level in each testing is a two-sided 0.05. If at any stage the null hypothesis H_0 is not rejected, then the formal testing procedure will stop.

Figure 4 Illustration of Delayed-Start Analyses Using Data from the Beginning of Period A of Study GN28352 to the End of Study Period B or OLE

[figure not shown]
[figure not shown]

Figure 5 Testing Hierarchy for Delayed-Start Analyses

API = Alzheimer's Prevention Initiative; ADAD = autosomal-dominant Alzheimer's disease; FCSRT = Free and Cued Selective Reminding Task.

Note: For a definition of H0 and H1, please see Section 2.

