Note that both \bar{T}_1 and \bar{T}_2 are treated as constants and are estimated from the data. A non-inferiority test with different margins will be applied ([Liu-Seifert et al. 2015](#)). A 90% CI will be calculated for $\Delta_2 - 50\%\Delta_1$ or $\Delta_2 - 30\%\Delta_1$, depending on the specified margin in the test; if the lower limit of the CI is greater than 0, then the H_0 will be rejected, meaning that by the end of the OLE at least 50% (or 30%) of the treatment effect at the end of Study Period A is preserved.

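### The delayed-start durations in SAP Appendix 3 are not tied to carriers who enter Period B, and catch-up starts at a different time from the model's slope change, so the retained-benefit test can err in either direction

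*SAP*

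**What the plan says.** SAP Appendix 3 defines the benefit at the end of Period A as Δ1 = βx·T1-bar. The benefit left at the end of the extension is Δ2 = (βx − βB)·T2-bar + βB·T1-bar, where βB is the slope change in former-placebo carriers. (The model prints two subscripts for this parameter; I take them as one.) For T1-bar, "we first calculate the arithmetic mean of duration in Study Period A"; for T2-bar, "we also calculate the arithmetic average of overall duration at the end of the OLE among mutation carriers". Both then enter the test as constants.

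No condition on entering Period B is attached to either mean. SAP Section 5.10.1 states that "the analysis population will be based on mITT", a set defined by one dose of study drug. Protocol Section 3.2.1 states that "Continuation into Study Period B is optional".

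In the model, the slope change for former-placebo carriers sits at T_i, defined as the first endpoint assessment after entry. Protocol Appendices 5 and 6 schedule the first Period B cognitive assessments at Week 25.

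The decision uses a 90% CI for Δ2 minus 50% or 30% of Δ1: "if the lower limit of the CI is greater than 0, then the" null is rejected, and the result is read as "at least 50% (or 30%) of the treatment effect at the end of Study Period A is preserved".

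**The concern.** Rearranged, Δ2 = βx·T2-bar − βB·(T2-bar − T1-bar). The gap between the means is the only route by which catch-up time reaches the decision. A carrier who leaves in Period A or declines Period B has the same duration in both means on the literal reading, adds no catch-up time, and is scored as having kept the whole benefit. Such a carrier supplies no information about a delayed start.

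The formula and the model also disagree on when catch-up begins. Δ2 starts it at the end of Period A. The model starts it at T_i, about half a year later.

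These are formal, alpha-controlled tests on both primary endpoints. SAP Section 5.10.1.2 says the Sponsor will be unblinded during Period B to analyse Period A, so the averaging set and time origin should be fixed beforehand.

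**Working it through.** **Inputs from the documents**
- 84 carriers per arm (SAP Appendix 2 simulation).
- At least 260 weeks in Period A, with Year 8 the longest (SAP Section 5.3.4).
- Snapshot 2 years after Period A (SAP Section 5.10).
- Period B cognitive visits at Weeks 25, 53, 77 and 105, taken as 0.5, 1.0, 1.5 and 2.0 years after the switch.
- Margins m = 0.5 and 0.3.

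**Assumptions**
- Non-entry of 25%, borrowed from the sample-size text ("Assuming a 25% dropout rate"). That is a planning figure for dropout, not an entry share.
- Dropout spread evenly over Period A; half-yearly visits.
- Random-intercept SD 5, random-slope SD 1, residual SD 4; βx of 0.6 to 1.0 points per year.
- The true slope change occurs at the switch.

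**1. The stated level.** A 90% CI lower limit above 0 rejects with P(Z > 1.645) = 0.050 one-sided, equivalent to 0.10 two-sided. SAP Section 5.10.1.1 says "The α level in each testing is a two-sided 0.05", so the 0.05 is reproduced only as a one-sided level. That mismatch is a separate point; 5% is the benchmark here.

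**2. Averaging set, slope change at the switch.** With k = βB/βx, retained fraction = [T2 − k(T2 − T1)]/T1.
- Entrants: T1 = 6.3, T2 = 8.3. Exactly 50% retained needs k = (8.3 − 0.5 × 6.3)/2.0 = 2.575.
- All carriers: T1-bar = 5.45, T2-bar = 6.94, gap 1.49 years (about 0.75 × 2.0).
- Formula with all-carrier means: (6.94 − 2.575 × 1.49)/5.45 = 3.10/5.45 = 57%.

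In general the excess over m is (1 − m)(1 − p·T1_entrants/T1_all), with p the entry share. Here it is 0.5 × (1 − 4.725/5.45), about 0.07. It is zero when p = 1.

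**3. Time origin.** If the slope truly changes at the switch but the model bends half a year later, visits at 0, 0.5, 1.0 and 1.5 years after T_i carry 0.5, 1.0, 1.5 and 2.0 years of catch-up. A rough least-squares slope through the origin, ignoring within-person correlation and holding βx fixed, is (0.5×1.0 + 1.0×1.5 + 1.5×2.0)/(0.5² + 1.0² + 1.5²) = 5.0/3.5 = 1.43 times the true βB. Δ2 then multiplies this steeper slope by the full gap.
- All carriers: k = 2.575 × 1.43 = 3.68; (6.94 − 3.68 × 1.49)/5.45 = 27%.
- Entrants: (8.3 − 3.68 × 2.0)/6.3 = 15%.

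Generalised least squares for the full random-slope model softens this to 31% and 20%.

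**4. Rejection rates when true retention among entrants is exactly 50%**

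| Slope change in model | Averaging set | Fraction returned | Rejection rate |
|---|---|---|---|
| At the switch | All carriers | 57% | 8.5–11.8% |
| At the switch | Entrants | 50% | 5.0% |
| T_i as printed | All carriers | 31% | about 1% or less |
| T_i as printed | Entrants | 20% | about 0.5% or less |

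**5. Second parametrisation.** This takes the planned 30% effect, CV 65% split evenly between slope and residual, and entrants at 6.5 and 8.5 years.
- Slope change at the switch, all-carrier means, m = 0.5: 5.0% at full entry, 6.0% at 90%, 8.3% at 75%, 15.2% at 50%.
- Across effects of 15–50%, extensions of 1–3.5 years and different variance splits, 75% entry gives 6.0–14.3%.
- Non-entrants who complete Period A but decline Period B, 75% entry: 16.1%.
- T_i as printed, 75% entry: 0.9% with early dropouts, 2.5% with completers who decline. At 50% entry with completers who decline it is 17.0%, so even with the printed T_i the direction is not fixed.
- With no effect in either period the rate is 5.0% whatever the means.

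**The case against.** The strongest reply is that the test keeps its level for the contrast it evaluates. The two means are constants, Δ2 is linear in them, and all-carrier means give an average over the mITT carriers if each non-entrant's benefit is taken as frozen at the last visit. Restricting to entrants conditions on a post-randomisation event. This stands as far as it goes: the fault is a mis-targeted hypothesis, and a reader who inferred a wrong error rate in every case would go too far. But the SAP states no frozen-benefit estimand, and its conclusion is worded as preservation of effect to the end of the OLE. The means only set the durations at which the contrast is evaluated; the model can still be fitted in mITT.

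A reader might also infer that the SAP includes non-entrants in both means, or that T1-bar covers all carriers and T2-bar only entrants. The documents establish neither. Non-entrants are not mentioned, and the second mean is introduced as parallel to the first over the same group, which fits the mixed reading poorly. Using carriers who have both durations is also possible.

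It is fair, too, that the inputs are not the trial's. With a standard error for βx of 0.18, effects of 0.6 to 1.0 are 3.3 to 5.6 standard errors, larger than the roughly 2.8 that goes with 80% power. The second parametrisation, at the planned effect, meets that objection.

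**Conclusion.** The point holds as an undefined averaging set combined with a mismatched time origin. With 75% entry and a true 50% retention among entrants, the same trial could return about 57% or about 31%, with rejection rates of 8–12% or about 1% or less, depending on where the model's slope change sits. A reader might infer that disease-modification claims are made too easily. The documents do not support that as a general statement, because with T_i as printed most scenarios give a rate below 5%. Nor does restricting the means to entrants repair the test alone: with T_i as printed it returns about 20%, further from the truth.

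All rates are scenario values, since the documents give no Period B entry share, no observed effect and no variance components for this model. If every carrier enters, the averaging set makes no difference, though the T_i mismatch remains. The primary Period A result is untouched, and if the study is terminated on that result SAP Section 5.10 makes all Period B analyses exploratory.

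**What to change.** In SAP Appendix 3:
1. Compute T1-bar and T2-bar, in years, over one named set: mutation carriers with at least one Period B or OLE assessment of the endpoint.
2. State how carriers who never enter are handled in Δ1 and Δ2.
3. Use one time point, the switch at the end of Period A, both for T_i in the model and for the start of catch-up in Δ2.
4. Keep the mITT carriers for fitting the model.

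Items 1 and 3 must be made together: in these scenarios the rate returns to 5.0% only when both are in place. The cost is a few sentences and no new data, provided they are settled before the two-year snapshot is analysed.

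### The delayed-start retention tests are set at a two-sided alpha of 0.05 in SAP 5.10.1.1 but decided on a 90% CI in Appendix 3, which is a two-sided 0.10 rule

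*SAP*

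**What the plan says.** SAP Section 5.10.1.1 restricts testing of the continuous extension endpoints to two of them: "statistical testing will be performed only on the API ADAD Composite Cognitive Test total score and the FCSRT Cueing Index". It sets up error control: "To control the type I error within the delayed-start analyses, the fixed testing sequence is specified in the following figure". It gives the level: "The α level in each testing is a two-sided 0.05". Testing stops at the first hypothesis that is not rejected. The note under Figure 5 adds: "For a definition of H0 and H1, please see Section 2". Section 2 holds the Period A no-difference hypotheses for the two primary endpoints.

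Appendix 3, under the delayed-start model, gives the rule for the retention tests: "A non-inferiority test with different margins will be applied". Δ1 is the average benefit at the end of Period A and Δ2 the average benefit remaining at the end of follow-up. Then: "A 90% CI will be calculated for" Δ2 − 50%Δ1 or Δ2 − 30%Δ1, according to the margin, with H0 rejected "if the lower limit of the CI is greater than 0". Rejection is read as at least that share of the Period A effect being retained.

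The protocol (Section 4.10.10) plans the delayed-start analysis but gives neither an alpha nor a confidence level for it.

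**The concern.** The two SAP sections describe the same tests and give different critical values. A two-sided test at 0.05 corresponds to a 95% CI and spends 0.025 in the direction of benefit. A rule that looks only at the lower limit of a 90% CI spends 0.05 in that direction. Nothing in the readable text says that 0.05 is meant as one-sided here. The 90% interval also stands apart from the rest of the SAP, which presents 95% CIs for the primary, sensitivity and supplementary analyses (Sections 5.3.3 to 5.3.5) and tests the key secondary endpoints at a two-sided 0.05 (Section 5.4.1).

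Two things are at stake. A retention claim could be made at a looser standard than the one stated. And because the sequence stops at the first non-rejection, one borderline result also decides whether later hypotheses are formally tested.

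**Working it through.** **Inputs**

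- Stated level of each delayed-start test: 0.05, two-sided (SAP 5.10.1.1).
- Interval used for the decision: 90% (SAP Appendix 3).
- Rejection: lower limit above 0, one direction only (SAP Appendix 3).
- Contrast: D = Δ2 − mΔ1 with m = 0.5 or 0.3 (SAP Appendix 3). The null boundary is D = 0.

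**Can the stated level be reproduced from the Appendix 3 rule?**

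Under normal theory, the lower limit of a 100(1 − a)% CI is above 0 exactly when Z = D̂/SE exceeds the 1 − a/2 normal quantile.

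- 90% CI, a = 0.10: reject when Z > 1.645. At D = 0 this has probability 0.050 in the direction of benefit, and 2 × 0.050 = 0.10 two-sided.
- 95% CI, a = 0.05: reject when Z > 1.960. At D = 0 this has probability 0.025 in the direction of benefit, and 2 × 0.025 = 0.05 two-sided.

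The stated two-sided 0.05 is therefore not reproduced by the 90% CI. It is reproduced by a 95% CI. Reading 0.05 as one-sided would make the 90% CI fit, but 5.10.1.1 says two-sided. The ratio of the error rates at the margin is 0.050/0.025 = 2.

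**Where the rules disagree.** Every result with Z between 1.645 and 1.960 (one-sided p between 0.025 and 0.05) counts as retained under Appendix 3 and not retained under 5.10.1.1.

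**Effect of a preceding step.** Figure 5 is not shown, so it is unknown whether a retention test follows a superiority test. As an assumption, a two-sided 0.05 test of Δ1 was placed before it. The simulation used 1,000,000 draws per scenario, the estimates of Δ1 and Δ2 with unit variance and correlation 0.3 or 0.7, and true Δ2 on the boundary for m = 0.5 and 0.3.

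| Setting | 90% CI | 95% CI |
|---|---|---|
| No preceding step | 0.050 | 0.025 |
| Preceding step, strong Period A effect (mean Z of 8) | 0.050 | 0.025 |
| Preceding step, weak Period A effect (mean Z of 2.8) | 0.033 to 0.049 | 0.016 to 0.025 |

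A preceding step can lower both rates, so 5% is an upper figure. The ratio stays near 2.

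**Power cost of a 95% CI.** If the power under the 90% CI is P, the power under the 95% CI is Φ(z_P + 1.645 − 1.960).

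- P = 0.80: Φ(0.842 − 0.315) = Φ(0.527) = 0.70.
- P = 0.90: Φ(1.282 − 0.315) = Φ(0.967) = 0.83.

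**The case against.** The best defence is that a 90% CI is a usual way to run a one-sided 0.05 non-inferiority test. On that view the chance of a false retention claim at the margin never exceeds 0.05, numerically the stated alpha, and the fault is one of sidedness in one sentence. This may well be the intent. It does not settle the matter, because the SAP says two-sided and does not say that these tests are an exception. A two-sided 0.05 leaves 0.025 for the favourable direction.

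Other limits on the point do stand. Four stronger readings are tempting, and the documents do not support them.

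- *The whole delayed-start family runs at double its level.* The steps of Figure 5 cannot be seen. Any superiority steps in it can properly be run at a two-sided 0.05, with no conflict.
- *The pointer to Section 2 is wrong.* Those hypotheses would be the right ones for superiority steps. What can be said is that Section 2 contains no retention hypothesis and no 50% or 30% margin.
- *This is the only formal testing in the extension, and it carries a disease-modification claim.* Section 5.10.1.2 also plans stratified log-rank p-values for two time-to-event endpoints. The delayed-start text claims only that a share of the Period A effect is preserved.
- *The sponsor would pick the level after seeing the data.* Appendix 3 does prespecify one explicit rule. The conflict leaves room for dispute, but nothing in the documents provides for a later choice.

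**Conclusion.** The plan is wrong as written for the 50% and 30% retention tests: the Appendix 3 rule does not deliver the level stated in 5.10.1.1, and no readable text reconciles the two. At the margin the false-claim rate in the direction of benefit is up to 5% instead of 2.5%, and results with z from 1.645 to 1.960 are decided differently by the two sections.

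This rests on normal theory for the contrast and on reading two-sided 0.05 in its ordinary sense. The scope is narrow. The Period A primary tests (0.04 and 0.01), the key secondary tests and any superiority steps in Figure 5 are untouched. If the sponsor terminates the study on the Period A results, SAP Section 5.10 makes all Period B analyses exploratory, and the conflict then matters less.

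**What to change.** Settle the level before the data snapshot planned for two years after the last Period A efficacy visit. There are two acceptable routes.

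1. In Appendix 3, change the 90% CI to a 95% CI and keep the requirement that the lower limit exceed 0. This delivers the two-sided 0.05 already stated in 5.10.1.1. The price is the power loss shown above: about 80% to 70%, or 90% to 83%.
2. If a one-sided 0.05 non-inferiority test is intended, keep the 90% CI, restate 5.10.1.1 as one-sided 0.05 for the retention tests only, and justify the looser level. This costs no power, but the 5% false-claim rate at the margin is then explicit and has to be defended.

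Under either route, add the retention hypotheses next to the Section 2 pointer, not in place of it: H0: Δ2 − mΔ1 ≤ 0 against H1: Δ2 − mΔ1 > 0, with m = 0.5 or 0.3. State which steps of Figure 5 are superiority tests and which are retention tests. The work is a few lines of SAP wording.
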